### **Missing data**

Any missing values throughout the follow-up period are inherently accounted for in the mixed model approach, but multiple imputation methods and complete case analysis will be applied in sensitivity analyses (see chapter 6.2 and 6.3 below for further details).

## **Section 5: Trial Population**

### **5.1 Eligibility**

Inclusion criteria were all patient between 18 and 75 years old with pain lasting longer than 6 months and who had undergone an extensive multidisciplinary examination at the four pain centers. However, it was only possible for those who lived in a relatively short distance from the hospital. Moreover, inclusion in the study was not offered to those who were receiving other individual treatment courses which could interfere with the effects of the group treatment the next 52 weeks after inclusion.

Exclusion criteria were severe somatic disease or severe mental disorder (ongoing mania, psychosis, suicidal ideation or substance abuse/addiction), not being able to communicate in Norwegian or in need of 24-hour personal assistance.

### **5.2 Recruitment**

The recruitment of participants was conducted in Trondheim, Oslo, Bergen and Tromsø. The recruitment started in March 2020, had to break because of COVID-19, and was completed in April 2023. Further details on recruitment are given in the registered protocol.

### **5.3 Withdrawal and follow-up**

Each participant was informed that they can withdraw from the study at any time, and that they then have the right to have any personal, health and questionnaire data deleted.

## Section 6: Analyses

### 6.1 Outcome definitions

All outcome variables described below are assessed at baseline, post-treatment, eight weeks, 16 weeks, 32 weeks and 52 weeks.

Primary outcome variable: Pain intensity measured by the Brief Pain Inventory(Cleeland & Ryan, 1994; Tan et al., 2004). The cut-off for clinically meaningful improvement is set to 2 points (Robert H Dworkin et al., 2008).

Secondary outcome variables: The primary outcome in the main RCT study is Pain interference measured by the Brief Pain Inventory (Cleeland & Ryan, 1994; Tan et al., 2004). Secondary outcomes include Physical Function and Social network by PROMIS(Garratt et al., 2021), anxiety and depression (Zigmond & Snaith, 1983).

### 6.2 Analyses methods

The primary analysis will estimate mean difference and 95% confidence interval (CI) in BPI pain intensity score at 52-week follow-up between the two intervention groups and control group (i.e., ACT vs. ACT with enhanced mindfulness or education). The analyses will be conducted according to the intention-to-treat principle using a linear mixed model for repeated measures. This model includes all available data for all participants at each time point (i.e. baseline, post-treatment, 8 weeks, 16 weeks, 32 weeks and 52 weeks). Further adjustment for baseline levels of potentially important prognostic factors, such as age, sex, socioeconomic status, pain duration, and pain intensity will also be conducted.

All secondary outcomes will be analysed using a similar approach; for continuous (or approximately continuous) we will use linear mixed models to estimate mean differences between groups, and for ordinal or binary variables we will use logistic GEE analyses to estimate odds ratios.

Possible modifiers of the effect of intervention on the primary outcome will be assessed in supplementary analyses stratified by sex, age groups, socioeconomic status, and accompanied by tests of statistical interaction to assess departure from additive effects (i.e., including a product term of group and modifier in the regression model).

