4. The four centers have a response rate on internet-based self-report on almost 100% pre-admission and about 80% one year after treatment from four identical online quality records. This self-report system will be used in the study and has been published as feasible by our research group (34).
5. It should be possible to identify patient characteristics (phenotypes) that can guide clinicians in the future in the selection of which of the patients are likely to profit from ACT, and which patients are likely to receive benefits from the addition of mindfulness training.
6. It should also be possible to identify patients who benefit less from the treatments and who may need other alternatives. Patient characteristics can help us to identify key target components in the development of new treatments for these patients.
7. The theoretical hypothesis aiming to identify a key mediator of change is based on modern cognitive neuroscience including thorough neurobiological studies of the human brain.
8. Both for self-report measures and attentional functioning the study will use safe computerized test systems the patients can complete in their homes. This will make it possible to increase the number of assessments without the subjects needing to return to the outpatient clinic. This will increase the quality of assessments and reduce the cost
9. Since the study includes self-report assessment methods that are easy to deliver and score, it is also easy to translate the knowledge and procedures to other treatment facilities in Norway and internationally after the project period.

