### 4.3 Analysis populations

The primary analysis will estimate mean difference and 95% confidence interval (CI) in BPI pain intensity score at post-treatment and 52-week follow-up between the two interventions and the active control group (ACT, ACT with enhanced mindfulness and education group). The analyses will be conducted according to the intention-to-treat principle using a linear mixed model for repeated measures. This model includes all available data for all participants at each time point (i.e. baseline, post-treatment, 16 weeks, 32 weeks and 52 weeks). The distribution of the BPI pain intensity score will be assessed, and the variable may be transformed (e.g. log transformation) to better fit with the assumptions for the regression analyses. In the regression model, individual participants will be specified as a random effect, accounting for the within subject covariance structure. The effect of group and time will be specified as fixed effects using a joint variable of intervention and time. Here, baseline levels are pooled over the three study groups assuming that any baseline differences are due to

chance; this also controls for any baseline differences in the outcome variable. The between group difference at 52-week follow-up will be adjusted for the variable used for stratification in the randomisation (i.e., center). Further adjustment for baseline levels of potentially important prognostic factors will also be conducted. We will also use GEE analyses to estimate an odds ratio (with 95% CI) for a two-point change in BPI between the groups taking into account the repeated observations. This analysis will be adjusted for the same factors as those included in the linear mixed model. In addition to the intention to treat analyses, we will conduct per protocol analyses using information on adherence to the trial.

All secondary outcomes will be analysed using a similar approach; for continuous we will use linear mixed models to estimate mean differences between groups, and for ordinal or binary variables we will use logistic GEE analyses to estimate odds ratios. For analyses of mean differences, the distribution of each outcome variable will be assessed to inform possible transformation or initiate alternative analytical procedures. The precision of all estimated effects will be assessed by a 95% CI.

Possible modifiers and mediators of the effect of intervention on the primary and secondary outcomes will be assessed in secondary analyses.

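### SAP 6.2 puts baseline pain into the further-adjusted pain-intensity model both as an outcome row and as a covariate; its 52-week standard error is then about 10%–15% too small (assumed correlation 0.4–0.8)

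*SAP*

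**What the plan says.** SAP 6.2 opens with the primary analysis of BPI pain intensity at 52 weeks, the only outcome named in that paragraph. The mixed model uses all available data "at each time point (i.e. baseline, post-treatment, 8 weeks, 16 weeks, 32 weeks and 52 weeks". Baseline pain is therefore one of the modelled outcomes. The same paragraph ends: "Further adjustment for baseline levels of potentially important prognostic factors, such as age, sex, socioeconomic status, pain duration, and pain intensity will also be conducted". Secondary outcomes come only in the next paragraph.

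SAP 4.3 describes the same model and lists five assessment times where 6.2 lists six. It pools the baseline means over the three arms and says that "this also controls for any baseline differences in the outcome variable". On covariance it says only that "individual participants will be specified as a random effect, accounting for the within subject covariance structure". On the main adjustment it says: "The between group difference at 52-week follow-up will be adjusted for the variable used for stratification in the randomisation (i.e., center"). For the two-point-change GEE it says: "This analysis will be adjusted for the same factors as those included in the linear mixed model".

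Neither section drops the baseline row from the further-adjusted model, exempts pain intensity when it is itself the outcome, or plans robust standard errors.

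**The concern.** A baseline outcome can be used in one of two ways: as a row of the longitudinal response with a common mean across arms, or as a covariate with follow-up rows only. Either gives a valid, ANCOVA-level analysis. Used together, they conflict. The covariate has a single slope. In the baseline row the outcome is the covariate itself, so the right slope is exactly 1; in the follow-up rows it is about the correlation rho. The fitted slope falls in between. The baseline row then has too little residual variation, the random-intercept variance is estimated too low, and the model-based standard error at 52 weeks shrinks.

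The further-adjusted interval would then be narrower than the center-adjusted one, and a reader could take that as confirmation of the primary result. In fact adding baseline pain in this way makes the estimate slightly less precise.

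**Working it through.** The plan states no standard error or correlation for this model, so there is no figure of its own to reproduce.

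**Inputs.** SD = 2.1 (variance 4.41) and n = 162 per arm, from SAP 3.3. J = 6 rows (SAP 6.2 list) or 5 rows (SAP 4.3 list). Constant correlation rho between assessments is an assumption, taken as 0.4 to 0.8. Random intercept, model-based standard errors, complete data, large-sample limit. The other prognostic factors are left out, to isolate baseline pain.

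**Formulas**, with s² = 4.41:

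1. Slope on baseline: g = [1 + (J − 1)rho]/J.
2. Residual variance: e = s²(1 − rho), the same with or without the covariate.
3. Random-intercept variance: t = s²(g − g²) − e/J. The value needed given baseline is s²(rho − rho²).
4. Weight on the baseline row: k = t/(t + e).
5. Reported SE² = (2/n)(t + e)(1 − k²).
6. Total weight actually put on baseline: c = g + k(1 − g). True SE² = (2/n)s²(1 − 2c·rho + c²).

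**Six rows, rho = 0.6.**

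- g = (1 + 3)/6 = 0.667
- e = 4.41 × 0.4 = 1.764
- t = 4.41 × (0.667 − 0.444) − 1.764/6 = 0.980 − 0.294 = 0.686, against 4.41 × 0.24 = 1.058 needed
- k = 0.686/2.450 = 0.28
- Reported SE = √[(2/162) × 2.450 × 0.9216] = 0.167
- c = 0.667 + 0.28 × 0.333 = 0.76
- True SE = √[(2/162) × 4.41 × (1 − 0.912 + 0.5776)] = 0.190
- Ratio 0.877; two-sided type I error 2[1 − Φ(1.96 × 0.877)] = 8.6%

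Without the covariate the weight on baseline is rho, and both SEs equal √[(2/162) × 4.41 × (1 − 0.36)] = 0.187: ratio 1.00, type I error 5.0%.

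**Five rows, rho = 0.6.** g = 0.680, t = 0.607, ratio 0.868, type I error 8.9%.

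**Range.** The last column is 162/ratio², the sample size per arm that the reported precision implies.

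| Rows | rho | Reported SE / true SE | Type I error | Implied n per arm |
|---|---|---|---|---|
| 5 | 0.4 | 0.895 | 7.9% | 202 |
| 5 | 0.6 | 0.868 | 8.9% | 215 |
| 5 | 0.8 | 0.847 | 9.7% | 226 |
| 6 | 0.4 | 0.905 | 7.6% | 198 |
| 6 | 0.6 | 0.877 | 8.6% | 211 |
| 6 | 0.8 | 0.855 | 9.4% | 222 |

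**With dropout.** The Protocol (section 2, methodological strengths, item 4) reports a response of "about 80% one year after treatment from four identical online quality records". Simulation used 8,000 null trials per setting, REML, center as a fixed effect, and monotone dropout reaching 20% at 52 weeks:

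| Rows | rho | No covariate | Covariate and baseline row | Covariate, baseline row dropped |
|---|---|---|---|---|
| 6 | 0.4 | 4.7% | 7.6% | 4.7% |
| 6 | 0.6 | 5.2% | 9.2% | 5.2% |
| 6 | 0.8 | 5.4% | 9.3% | 5.3% |
| 5 | 0.6 | 5.4% | 9.6% | 5.4% |

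The mean estimate was within 0.002 of zero. Only the combination fails.

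**Unstructured covariance.** This does not rescue the model. The baseline residual is (1 − slope) × baseline, so the log determinant of the residual covariance equals its value at slope 0 plus 2·ln(1 − slope). With five rows and rho 0.6 it is 4.98 at slope 0, 4.98 − 9.21 = −4.23 at slope 0.99, and −18.05 at slope 0.99999. The likelihood has no maximum as the slope approaches 1.

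**The case against.** **The list gives examples.** Pain intensity is one illustration among several, and an analyst who has read in SAP 4.3 that pooling already handles baseline might leave it out. The wording may also be carried over from another outcome: SAP 6.1, under the secondary outcomes, calls pain interference the primary outcome of the main trial, and baseline pain intensity is a sound covariate for that. This explains how the item may have got there. It does not change what the paragraph says for the outcome it names.

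**The size is conditional.** It needs the covariate entered, the baseline row kept, a random intercept, model-based standard errors and a fairly high correlation. This stands. At rho = 0.3 the ratios are 0.911 (five rows) and 0.921 (six), a shortfall of 8%–9%. If an unstructured covariance were fitted instead, the analyst would meet a visible failure rather than a quietly narrow interval.

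**The analysis is supplementary and the effect is modest.** This also stands. At rho = 0.6 with six rows the 95% half-width is 1.96 × 0.167 = 0.33 reported against 1.96 × 0.190 = 0.37 true. The rejection rates above belong to this model, not to the trial's main test. For scale, the design difference between adjacent arms is 10% of 5.4, or 0.54 points.

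**The other covariates are left out.** Age, sex, socioeconomic status and pain duration could genuinely narrow the interval. The comparison of 0.190 with 0.187 therefore describes adding baseline pain alone, not the whole further-adjusted model.

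**Conclusion.** The concern holds. Followed as written, SAP 6.2 produces a further-adjusted pain-intensity model whose 52-week standard error is about 10%–15% too small and whose nominal 5% test rejects 7.6%–9.7% of the time under the null. These figures assume a constant correlation of 0.4–0.8, a participant random intercept, model-based standard errors and complete data; the simulations with 20% missing at 52 weeks agree. The correlation is an assumption, because the documents give none. The point estimate stays unbiased, and the center-adjusted estimate is free of this fault. The change should be made because the error is one-directional, concerns the primary outcome and is free to remove. It does not undermine the main analysis.

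**What to change.** Add one clause to SAP 6.2: baseline pain intensity is not a covariate in the mixed model for pain intensity and enters only through the pooled baseline row. Alternatively, drop the baseline row from the further-adjusted model and keep the covariate. The first option keeps 6.2 consistent with 4.3.

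Do not delete the item everywhere. It is a legitimate covariate for the other outcomes. It is also legitimate in the two-point-change GEE, which analyses change from baseline; because SAP 4.3 ties the GEE's adjustment factors to those of the mixed model, the clause should say that the exclusion does not carry over.

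The cost is one sentence: no new data, visits or software, and no loss of precision, since the pooled baseline row already gives the ANCOVA-level standard error (0.187 at rho 0.6).

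A separate, conditional point: SAP 4.3 names no residual structure. If a random intercept alone is fitted and the correlation falls with time, the center-adjusted standard error is also too small; type I error was 6.4%–10.0% over three assumed patterns of decay. An unstructured residual covariance would remove that dependence, at 5 × 6/2 = 15 parameters for five times or 6 × 7/2 = 21 for six, but it can be fitted only once the baseline covariate is out.

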### 6.3 Missing data

Any missing values are inherently accounted for in the mixed model approach, but multiple imputation methods will be applied in sensitivity analyses. Multiple imputation will include factors that predict missingness of a specific factor, as well as all factors that are included in the main model (outcome, intervention, or adjustment variables). The number of imputed datasets will be guided by the number of missing observations for each variable, but we aim at using a minimum of 10 imputed datasets for each variable.

### 6.3 Harms

As stated above, no harms are expected, and thus we do not plan any specific analyses for this. If any study related harms should occur, these will be described and reported.

### 6.4 Statistical software

All analyses related to the primary outcome will be conducted using Stata.

